#### *3.3.1. Pre-screening phone call visit*

The purpose of the pre-screening phone call visit is to quickly determine if potential participants fit within the study's core inclusion criteria (age and BMI) and doesn't meet some of its permanent exclusion criteria (e.g. morbidities, pregnancy, known allergies, etc.). Only participants with existing blood exams carried out in the previous 3 months or able to obtain a prescription of blood tests required for the assessment of the eligibility for the study will be evaluated. Once a potential participant is cleared through the pre-screening visit and confirms interest in participation, they may proceed through the screening visit.

#### *3.3.2. Screening visit*

The purpose of the screening visit is to definitely determine volunteer eligibility for study participation. Subjects will be screened for eligibility for the study, ascertaining that all inclusion and exclusion criteria are met. Once participant met all inclusion/exclusion criteria, will be offered by study staff the opportunity to learn more about the research opportunity before any procedure is performed. Screening will include measurement of height, weight, and vital signs (body temperature, blood pressure, pulse, respiratory rate), completion of medical history questionnaire, review of medical history and current medications, assessment of sleep quality and disturbances with the Pittsburgh Sleep Quality Index (Appendix G) and the risk associated with sleep apnea with the Berlin Questionnaire (Appendix H), and collection of fasting blood (12 mL: 6 mL for serum, 6 mL for plasma). Blood testing will include: complete blood count (CBC), glycated hemoglobin (HbA1c), glucose, insulin, lipid profile (total cholesterol, LDL-cholesterol, HDL-cholesterol and triglycerides), AST (GOT), ALT (GTP), alkaline phosphatase, creatinine, reactive C protein (PCR), albumin, insulin, IGF-1, IGFBP1, homocysteine as well as a urine pregnancy test in females of child-bearing potential. Blood exams carried out in the last 3 months will be considered valid for the ascertaining of the inclusion/exclusion criteria. Fasting is defined as 12 hours of refraining from consumption of food and beverages though unlimited consumption of water is allowed and encouraged. Upon review of screening data acceptable for inclusion, an in-person or telephone interview with a study investigator (or designated staff) will be completed to confirm eligibility, and document absence of contraindications to participation. During this visit, ring sizes of participants will be obtained for all fingers, from which a ratio of appropriate ring sizes for this population group will be established. Participants will be then randomised into either one of the intervention arms (LD+FMD or LD) or in the control arm using a web-based randomisation system that will be controlled by the researchers of the Valter Longo Foundation in Milan (see section 8.1)

#### *3.3.4. Visit 2 (after three months or 5-7 days after the second FMD cycle, T1)*

After 3 months from the randomization, subjects in the arm 1 and 2 will be contacted to receive the FMD boxes for the second and the third FMD cycles, respectively, together with the ketone test strips to self-monitor urinary ketone bodies during the FMD cycles. Visit 2 will also include body composition assessment using Bioelectrical Impedance Analysis (BIA), measurement of height, weight, and vital signs and to assess sleep quality and disturbances with the Pittsburgh Sleep Quality Index (Appendix G) and the risk associated with sleep apnea with the Berlin Questionnaire (Appendix H).

#### *3.3.5. Visit 3 (after six months or 5-7 days after the third FMD cycle, T2)*

Subjects will meet with the study staff. During the clinical visit, staff will assess for signs and symptoms of adverse events, review compliance to the diet programs. Visit 3 will also include body composition assessment using Bioelectrical Impedance Analysis (BIA), measurement of height, weight, and vital signs, medical history and current medications and a collection of fasting blood for both hematological and genetic analyses as previously described for the baseline visit (see Table 1). Only subjects that received the Oura Ring device at the baseline visit will also receive an Oura Ring device for the continuous monitoring of sleep state and wakefulness for a 2-week period as previously mentioned. After this period, study staff will assess sleep quality and disturbances with the Pittsburgh Sleep Quality Index (Appendix G), the risk associated with sleep apnea with the Berlin Questionnaire (Appendix H) and will answer any questions from the subject. At this point, subjects belonging to the control arm will be given an opportunity to follow a LD program for a 6-month period (optional).

#### *3.3.6. Visit 4 and 5 (month 9 and 12, optional)*

Subjects belonging to the arm 3 that will decide to follow a LD program for a 6-month period will meet with the study nutritionist. During the clinical visit at month 9 (optional visit 4) and month 12 (optional visit 5), staff will review compliance to the LD diet and answer any questions from the subject.

### 3.4. *Additional assessments*

#### 3.4.1. *Exploratory Genetics: Telomere length*

The study includes genetic sample at the screening visit (see Table 1) that requires a separate informed consent form if the participant agrees to participate.

Exploratory genetic research studies are planned following study completion with the objectives of evaluating the impact of the two nutritional programs on telomere length used as a biomarker of individual ageing.

#### 3.4.2. *Oura Rings*

The study will also include a continuous monitoring of sleep state and wakefulness by providing Oura Ring devices: the rings are already documented in the literature for their potential in the measurement of sleep parameters with results comparable to polysomnography, the gold standard for the assessment of sleep disturbances, but making it also available on a larger scale and for a longer period of time (The Sleep of the Ring: Comparison of the ŌURA Sleep Tracker Against Polysomnography; *Behav Sleep Med.* Mar-Apr 2019;17(2):124-136.). The ring is a "sleep tracker" that comes in different sizes (US standard ring size 6–13), it is waterproof, weights approximately 15 g and its battery life lasts approximately 3 days. It automatically connects via Bluetooth and transfers data to a mobile platform in the dedicated App. The ring continuously collects data and processes them through an algorithm, to determine the stages of sleep (wakefulness, "light", "deep" and REM sleep): each night it monitors the latency sleep onset, time spent in "deep sleep", time spent in "light sleep", total time spent asleep and periods of wakefulness after starting sleep. It also adds information regarding sleep patterns, an analysis of heart rate and its variations, physical activity and body temperature. Oura ring fulfils the essential requirements of the applicable CE marking directives and regulations.

The design plans to randomly allocate 20 rings among 90 subjects in the 3 study groups that will result with sleep problems at the screening visit on the basis of the score obtained at the Pittsburgh Sleep Quality Index questionnaire (Appendix G). These three study groups will be balanced for age, sex, BMI and for the score obtained at the Pittsburgh Sleep Quality Index. The continuous monitoring of each parameter and sleep marker will last over a 2-week period. At each check point, questionnaires will also be distributed to assess sleep quality and disturbances with the Pittsburgh Sleep Quality Index (Appendix G) and the risk associated with sleep apnea with the Berlin Questionnaire (Appendix H).

### 3.5. *Prohibited Medications and Procedures*

No concomitant prescription medications, over-the-counter medications, medical foods, and nutritional supplements are to be started or doses changed during the study unless they are prescribed by the PI (or the subject's primary care giver) for treatment of a specific clinical event.

### 3.6. *Rescue Medications*

Acetaminophen, may however, be used for mild headache or myalgia at a dose of 650 mg three times daily as needed.

### 3.7. Subject Compensation

Subjects will not be compensated for participation in this trial.

## 4. Study Product: Formulation, Packaging, Labeling, Preparation, Administration, and Dosage of Study Products

### 4.1. Arm 1 (FMD plan)

The subjects will be instructed to follow their usual diet plan, except for 5 days when they eat the foods in the FMD box. The FMD diet is made up of *nut* bars, dehydrated soups, tea, olives, kale crackers, electrolyte beverages, and a chocolate crisp bar.

- Nut bars: Almond, macadamia nuts, pecans, vegetable inulin fibre (chicory root fiber), honey, coconut flour, flaxseed, natural flavour, sea salt, rosemary extract.
- Almond and Kale crackers: almonds, sesame seeds, tapioca flour, chia seeds, golden flax seeds, sunflower seeds oil, kale, sea salt, coconut sugar, coconut vinegar, onion powder, chili pepper, cumin seeds, black pepper, antioxidant: extract rich in tocopherol, garlic, origan, acidifier: citric acid.
- Electrolyte beverages containing water, natural vegetable glycerin, natural flavor,
- Olives.
- Spearmint tea, spearmint lemon tea, hibiscus tea.
- There are 5 different soups, which contain various combinations of rice flour, rice starch, potato flakes, tomato concentrate, sweet red pepper, basil, onion, leek, extra virgin olive oil, parsley, peas, yeast extract, savoy cabbage, carrot, garlic, spinach, celery, turmeric, black and white beans, champignon mushroom powder: minestrone, mushroom, tomato, vegetable, black beans soup;
- Chocolate crisp bar: inulin, almond butter, brown rice, cocoa powder, almonds, chocolate chips (brown sugar, cocoa mass, cocoa butter), rolled oats, brown rice syrup, flaxseed oil, rice dextrin, grape juice, salt.

In order to evaluate adherence to the FMD and its metabolic effects, patients in arm 1 will receive ketone test strips together with each FMD kit to self-monitor urinary ketone bodies.

#### 4.1.1. Study Product Storage and Stability

Subjects in the arm 1 will be given one box of FMD at the end of the baseline visit and other 2 boxes before the starting of the other FMD cycles during the study. Subjects in the arm 2 (FMD+LD) will be also given a copy of the longevity diet at screening visit. Information on the respective diet plans will be given to subjects after the screening visit. The study products will be handled and dispensed to subjects at ambient temperature at the study site according to good clinical practices.

#### 4.1.2. Study Product Accountability Procedures

It is the responsibility of the PI to ensure that a current record of study product disposition is maintained at the Study Site, and that records and logs include:

- amount of study product received and placed in storage area;
- dates and initials of individual responsible for investigational product inventory entry/movement;
- amount dispensed to and returned by each subject, including unique subject identifiers;
- amount transferred to another area for dispensing or storage;
- non-study disposition (e.g. lost, broken, wasted);
- amount destroyed at the site (if applicable).

The unused study products for this study will be disposed of according to good clinical practices.

#### 4.2. *Arm 2 (FMD + LD plans)*

The subjects will be instructed to follow their longevity diet plan, except for 5 days when they eat the foods in the FMD box. Subjects in the arm 2 will be instructed to follow a longevity diet based on these following prescriptions:

- vegan based diet with the addition of fish 2-3 times a week, choosing fishes with lowest mercury content;
- protein content should be 0.8 grams per day per kilogram of weight (most of the protein coming from vegetables and legumes and only some from fishes);
- monounsaturated and polyunsaturated fats are predominant and only very few amounts of saturated and trans-fats are allowed;
- complex Carbohydrates from vegetables, whole grains and legumes;
- addition of vitamins, minerals and EPA, DHA (Omega3) fats;
- food selected between the traditional food consumed by our grandparents and ancestry;
- time-restricted feeding. All food must be consumed within 12 hours each day.
- for those that are overweight or are nearly overweight (BMI >24), substitute either lunch or dinner with a low calorie, low sugar snack (approximately 100 kcal: salad, nuts, fruit, etc.).

The subjects will be instructed to follow the FMD program with the same procedures previously described for participants in the FMD arm. Also in this case, in order to evaluate adherence to the FMD and its metabolic effects, patients will receive ketone test strips together with each FMD kit to self-monitor urinary ketone bodies.

#### 4.3. *Arm 3 (control group)*

Participants in the arm 3 will undergo the same testing measures as the intervention groups and will be recommended to continue their usual diet. Participants belonging to this group will be given an opportunity to follow a 6-month LD program at month 6 with two additional (optional) visits at month 9 (visit 4) and at month 12 (visit 5).

#### 4.4. *Potential Risks*

There is a possibility, however, that a subject could be sensitive to food ingredients in one or more of the food formulas and have an allergic or intolerance reaction. Potentially serious reactions may include face and

throat swelling, trouble breathing, anaphylaxis (shock), convulsions, and death. Such reactions are possible if a subject has an intolerance or allergy (known or unknown) to the ingredients in the FMD. Longevity diet will be based on a selection of the traditional food of Southern Italy and thus the possibility of allergic reactions is very low.

#### *4.5. Potential Benefits*

The FMD is designed to achieve the beneficial effects of fasting while providing micronutrient nourishment (vitamins, minerals and others) of which the body is deprived during fasting. It minimizes the psychological burden of pure fasting. The Longevity diet has the advantage of being easy to follow as a lifestyle element, with appropriate foods being available in multiple venues. The subjects will receive extensive medical testing and these results will be available to the subjects after completion of their participation for their ongoing care.

#### *4.6. Assessment of Subject Compliance with Study Product*

Compliance will be measured using both a subject calendar provided by the investigator and direct verification of consumption of the FMD and adherence to the Longevity diet. Subjects will not be asked to return FMD boxes.

### **5. Description of Specific Testing Modalities**

#### *5.1. Hematological analyses*

Complete metabolic and lipid panels (overnight fasting) will be completed at the Istituto Clinico “[name]. R. De Blasi” srl, [name], in Reggio Calabria and analyzed immediately after the blood draw of each visit. Clinical and biochemical evaluations include lipid profile (total cholesterol, LDL-cholesterol, HDL-cholesterol and triglycerides), serum/plasma, albumin, alkaline phosphatase, insulin-like growth factor 1 (IGF-1), Insulin-like growth factor-binding protein 1 (IGFBP1), insulin, C-reactive protein (CRP), aspartate aminotransferase (AST), alanine aminotransferase (ALT), homocysteine, glucose, glycosylated hemoglobin (HbA1c).

#### *5.2. Blood collection and storage*

Blood samples will be collected and stored for future biomarker analyses. In particular, two 6.0 ml ethylenediaminetetraacetic acid tube of whole blood samples will be collected for each participant. One tube will be spun at 1300 g for 20 minutes at room temperature to generate supernatant (plasma), buffy coat and red blood cells which will be individually aliquoted into 1 ml, polypropylene, cryovials and stored at -80 °C for later analysis. The other 6.0 ml tube of whole blood will individually aliquoted into 1 ml and stored at -80 °C for later analysis as previously mentioned (see Table 1 and Figure 1).

#### *5.3. Blood Pressure Measurements*

Subjects will not consume any caffeine or alcohol or use tobacco products within 6 hours of the blood pressure measurement. Subjects will have their blood pressure measured using a mercury

sphygmomanometer on each visit. Subject's blood pressure will be measured in the left arm sitting position three times at 2-minute intervals following the American Heart Association (AHA) guidelines for blood pressure measurement. Heart rate will be measured with each blood pressure measurement.

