### 2.2. Endpoints

[figure not shown]
2.2.1. *Primary endpoint*: change from baseline to end of study in body composition measured as percentage of fat mass.

2.2.2. *Secondary endpoints*: change from baseline to end of study in blood pressure, serum lipids, glucose, HbA1C, CV biomarkers (body weight, BMI, blood pressure, serum lipid levels and dysglycemia blood measurements), body weight, BMI, insulin resistance, telomere length, proportion of participants who receive antihypertensive/hypoglycemic medications, and sleep quality and duration using the Pittsburgh Sleep Quality Index, and the Berlin questionnaire.

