## **7. Statistical Analysis plan**

### *7.1. Study Randomization*

This is a randomized, open-label three-arm exploratory study. After the screening visit, participants will be randomized through a pre-stratified randomization method to achieve balance between the three groups

(interventions and control group) according to baseline characteristics (covariates) that include gender, age (30-50; 51-65), and BMI (25-29,9; 30 and over) obtaining 8 strata. The block-based randomization will be then performed separately within each layer using a web-based randomisation system (<https://www.project-redcap.org/>) that will be controlled by the researchers not involved in the study from the Valter Longo foundation in Milan.

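### Blood pressure, a secondary endpoint, is read by an observer on a mercury device in an open-label trial with no masked reader; an automated device that stores its readings would be cheap protection.

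*Protocol*

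**What the plan says.** Protocol section 5.3 fixes the device and how often it is used: "Subjects will have their blood pressure measured using a mercury" "sphygmomanometer on each visit". It also fixes the procedure: "measured in the left arm sitting position three times at 2-minute intervals following the American Heart Association (AHA) guidelines". It does not say who takes the reading or whether that person is kept unaware of the arm.

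Section 7.1 gives the design: "This is a randomized, open-label three-arm exploratory study". The only independence it states concerns control of the randomisation system, not the measurement of outcomes.

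Section 2.2.2 makes blood pressure a secondary endpoint: "change from baseline to end of study in blood pressure, serum lipids, glucose, HbA1C, CV biomarkers". Section 7.7.2 compares arms 1 and 2 with arm 3 on that change, counts elevated blood pressure among the five metabolic-syndrome conditions, and uses baseline SBP and DBP as stratifiers.

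On the work of visit staff:
- Randomisation is described at the end of the screening visit (3.3.2).
- At T0, arms 1 and 2 receive their FMD boxes and diet instructions, and vital signs are taken at the same visit (3.3.3).
- At visit 3, where vital signs are taken again, section 3.3.5 says: "During the clinical visit, staff will assess for signs and symptoms of adverse events, review compliance to the diet programs".

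**The concern.** A mercury reading depends on the observer's judgement of when sounds appear and disappear and of where the column stands. In an open-label diet trial, an observer who knows the arm and expects the diets to lower pressure can shade readings without meaning to. Section 7.7 itself describes the data review as meant to show favourable changes, so the expected direction is on record.

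If this happens, the difference between a diet arm and control contains an artefact that no later analysis can separate from a diet effect. The other main measurements are less exposed: fat mass comes from a bioimpedance scale (5.4) and the blood markers from a laboratory (5.1). Blood pressure stands out because its value rests on a staff member's reading, and a change of device would cure that.

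**Working it through.** **Step 1. Can the reader know the arm?** Allocation precedes T0 (3.3.2, 7.1). Staff dispense boxes at T0 (3.3.3), review compliance with the study product at clinical visits (3.3) and review diet compliance at visit 3 (3.3.5). Blood pressure is measured at these same visits (5.3, Table 1). No section names a masked or separate reader. Awareness is therefore possible and plausible, but it is inferred; no sentence states it.

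**Step 2. Which shading matters?** The endpoint is a change from T0 to month 6. Let s be the average shading at a given visit in a given arm. The bias in the contrast is

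b = (s at month 6 − s at T0, diet arm) − (s at month 6 − s at T0, control arm).

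Shading that is equal at T0 and month 6 within each arm gives b = 0. Only a net difference in the change counts.

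**Step 3. Inputs.**
- The plan has no blood pressure power calculation to reproduce. Its sample size (7.4) is for fat mass. The 107 per group does reproduce: with f = 0.10, correlation 0.5, three groups and two time points, power at 107 is 0.902. Likewise 107/0.70 = 152.9, rounded up to 153.
- Completers per arm: 167 × 0.70 = 116.9, taken as 117 (enrolment and dropout from 7.4).
- SD of systolic change: not in the protocol; 10, 12 and 15 mmHg are assumed.
- Net differential shading b: not in the protocol; 1, 2 and 3 mmHg are assumed.
- True effect zero, two-sided 5% test, one diet arm against control. A simple two-mean test of change stands in for the mixed model of 7.7.2.

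**Step 4. Formulas.** SE = SD × √(2/117). Rejection rate = P(|Z + b/SE| > 1.96).

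Worked case, SD 12 and b = 2: SE = 12 × 0.1307 = 1.57; b/SE = 1.27; the rate is 0.247.

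| Assumed SD (mmHg) | SE | b = 1 | b = 2 | b = 3 |
|---|---|---|---|---|
| 10 | 1.31 | 12% | 33% | 63% |
| 12 | 1.57 | 10% | 25% | 48% |
| 15 | 1.96 | 8% | 18% | 33% |

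**Step 5. Sensitivity to the number analysed.** For b = 2 at SD 10, 12 and 15, the rates are 31%, 23% and 16% with 107 per arm, and 45%, 33% and 23% with all 167. A larger sample makes a fixed bias more likely to reach significance.

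**The case against.** The strongest reply has four parts.

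First, a reader might infer that every reading after randomisation is taken by someone who knows the arm. The protocol does not support that. It speaks of staff in general. It does not say that the person who reads blood pressure also dispenses boxes or reviews compliance, and it does not give the order of tasks within a visit. This stands: the claim must be that the reader may know the arm.

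Second, awareness already at T0 looks as if it makes matters worse. For a change score it need not, because shading that is constant over time cancels (step 2). This stands too, and limits the concern to differential shading.

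Third, the percentages follow from chosen inputs. They show how little shading would be needed, and do not show that it would occur. Section 5.3 also narrows the observer's discretion: "Subject's blood pressure will be measured in the left arm sitting position three times at 2-minute intervals", under a named guideline. That has some weight, but repetition reduces random error and leaves a systematic shift in place.

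Fourth, this is one secondary endpoint among many in a study that calls itself exploratory, and nothing in 5.3 is contradictory or miscalculated. That is fair, and it sets the priority. It does not remove the point, because the device is fixed in the protocol and is easily changed.

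A reader might also want to average screening and T0 blood pressure as the baseline, since the screening reading precedes allocation and averaging might add precision. The documents do not support this:
- The correlation of 0.5 in 7.4 is assumed for fat mass, not blood pressure.
- A screening reading can be the one that qualifies a participant (3.1.1), so averaging it in would bring regression to the mean into within-arm change.
- Section 4.1.1 gives arm 2 the Longevity Diet copy at screening and 3.3.3 gives the material at T0, so it is unclear that T0 precedes that diet.
- Averaging does nothing about the reading at month 6.

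**Conclusion.** The concern holds in limited form. The protocol prescribes an observer-read device in an open-label trial, names no masked reader, and uses the result as a secondary endpoint and as a component of metabolic syndrome. Differential shading between T0 and month 6 could bias the comparisons of arms 1 and 2 with arm 3.

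The size of that bias cannot be known from the document. At an assumed SD of 10 to 15 mmHg and about 117 completers per arm, a net 2 mmHg would raise the false-positive rate of one comparison from 5% to about 18% to 33%. This illustrates sensitivity and is not a forecast of the trial's error rate.

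The primary endpoint (fat mass by bioimpedance) and the sample size are not touched. The point is a worthwhile, inexpensive improvement rather than an error in the plan.

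**What to change.** In section 5.3, replace the mercury sphygmomanometer with a validated automated device that takes and stores the three readings. State that their mean is the value used, and that the same device type is used at all visits and in all arms. The existing conditions (left arm, seated, 2-minute intervals, AHA procedure) can stay as written.

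The cost is the purchase of a few devices, a wording change, and the discipline of keeping one device type throughout. No extra visit, staff or procedure is needed. The change should be made before endpoint readings begin, because shading in readings already taken cannot be removed in the analysis.
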